## Per-Protocol Analysis of UPCR

The primary analysis of UPCR during the double-blind period will be run using the Per-Protocol population.

## Responder Analyses

The response rate across dose groups for patients achieving 30% reduction in UPCR (whenever available 24-hour urine evaluations will be used) from baseline at Week 12 will be calculated, with the number of subjects in the respective treatment group in the ITT (or PP) population being the denominator. The 90% Clopper-Pearson exact CIs will be estimated for the response rates in each treatment group. The estimated difference and its associated 90% CIs of response rates between each of the CCX140-B (5, 10, or 15 mg) groups and the placebo group will be provided using stratified analysis using the Newcombe hybrid-score method. The Stratification factors are the same as used in the randomization: UPCR  $<3.5$  g protein/g creatinine versus UPCR  $\geq 3.5$  g protein/g creatinine at baseline and by the current use of glucocorticoids and/or immunosuppressive medications (yes vs no) if there are enough responders. If there are not enough patients in any strata, the stratification variable will be removed from the model.

Non-responder imputation for non-allowed medications:

All subjects who started new therapy or increased the doses of an existing therapy that is clinically significant and was not allowed per protocol will be imputed as non-responders for the responder analysis. For example, the new use or clinically significant increase doses of an angiotensin converting enzyme (ACE) inhibitor, angiotensin receptor blocker (ARB) or other blocker of the renin angiotensin aldosterone system (RAAS) or new use of glucocorticoids, a calcineurin inhibitor or other immunomodulatory or immunosuppressive therapy will be reviewed before database lock.

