### 3.4.1 Primary Efficacy Endpoint

#### UPCR Change from Baseline

The primary efficacy endpoint (UPCR) will be summarized by treatment group over time using descriptive statistics. Spaghetti plots of UPCR as well as percent change of UPCR (derived from morning void spot urine. If missing 24 hour urine evaluations will be used, if available) from baseline to weeks 4, 8, 12, 13, 16, 20, 24, and week 28 (if available) will be produced by treatment group and for all individual patients for visual inspection. Additionally, percent change of UPCR from week 12 to week 13, 16, 20, 24, and week 28 will be summarized by prior treatment group during the open-label period. The same analyses of for UPCR will be performed at baseline, week 12 and week 24 solely using UPCR values derived from 24-hour urine evaluations (missing assessments will not be replaced with morning void spot urine values).

The primary analysis will use the morning void spot urine results. If baseline or post-baseline morning void spot urine results are not available, 24 hour urine results will be used where available. Please note 24-hour urine assessments at Day 1, Week 12 and Week 24 were added after Protocol Amendment 4.0.

For inferential analysis of the ratio to baseline, UPCR will be loge-transformed to alleviate skewness of the data since data are not normally distributed. A mixed effect model for repeated measures (MMRM) will be performed in the ITT population with treatment, group, visit, and treatment-by-visit interaction as factors and baseline value and age as covariates. Least squares mean differences and the corresponding 90% confidence intervals (CI) between each of the CCX140-B (5, 10, or 15 mg) groups and the placebo group will be back transformed to the original scale. Corresponding P-values will also be presented.

In the MMRM model, missing data will not be imputed. This analysis is unbiased under the missing at random (MAR) assumption. Toeplitz covariance matrix will be used to model within-subject variance-covariance structure for the model errors. If the model does not converge using the Toeplitz covariance matrix, AR(1) covariance matrix will be used. If convergence is still not met, then compound symmetry (CS) will be used.

The code used to generate the MMRM analysis will be similar to the following:

```
*****
Note:
TRT01AN = randomized treatment group (numeric):
    1=Placebo, 2=CCX140-B 5 mg, 3=CCX140-B 10 mg, 3=CCX140-B 15 mg
VISITN = Visit Number

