## Sensitivity analyses

1. Given the high variability in morning void spot urine UPCR values, the baseline will be defined as the average of the screening and Day 1 morning void spot urine UPCR values if both are available. The UPCR analyses will be repeated using this baseline definition. If only one of 2 morning void spot urine values is available, that value will be used as the baseline. Post-baseline assessments will use the same approach as for the primary analysis prioritizing morning void spot urine and replacing missing assessments with 24 hour urine results where available.
2. As 24-hour urine evaluations were not available for all subjects. The following analysis will be conducted:
  - Baseline will be calculated by averaging the screening and Day 1 values using 24 hour urine results where available.
  - Post baseline assessments will prioritize the 24 hour results where available. Spot urine values will be used when 24 hour assessments are not available.
3. A sensitivity analysis will be conducted using the same approach as the primary analysis, however, for subjects who have been identified as taking non-allowed medications, all data after the initiation of the non-allowed medication will be imputed using the last observation prior to the initiation of the non-allowed medication.

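### The SAP's 30% UPCR responder analysis does not require the same urine specimen type at baseline and Week 12

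*SAP*

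**What the plan says.** The Responder Analyses paragraph of SAP 3.4.1 counts subjects "achieving 30% reduction in UPCR (whenever available 24-hour urine evaluations will be used) from baseline at Week 12". The parenthesis is the only specimen rule for this table. SAP 3.1.3 defines baseline as the last pre-dose value and does not mention specimen type.

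The main UPCR analysis in the same section has the opposite priority: "The primary analysis will use the morning void spot urine results", with a 24-hour result substituted if the void is missing. SAP 6 describes the responder analysis as an addition for the primary endpoint.

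On availability, SAP 3.4.1 states: "Please note 24-hour urine assessments at Day 1, Week 12 and Week 24 were added after Protocol Amendment 4.0". Sensitivity analysis 2 opens with "As 24-hour urine evaluations were not available for all subjects".

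Two other places show how the SAP writes specimen rules when it spells them out. The 24-hour-only repeat of the UPCR change analyses forbids substitution: "missing assessments will not be replaced with morning void spot urine values". Sensitivity analysis 2 sets the specimen separately at each end: "Baseline will be calculated by averaging the screening and Day 1 values using 24 hour urine results where available", and then "Post baseline assessments will prioritize the 24 hour results where available". The responder paragraph does neither.

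**The concern.** A percentage reduction is a ratio, and any systematic difference between the two specimen types cancels only if both ends use the same type. As written, a subject with a morning-void baseline and a 24-hour Week 12 collection can be classified on the mixed ratio. So can a subject with the reverse pattern. Two programmers following the paragraph could classify the same subject differently.

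The pattern is plausible. Someone dosed before the 24-hour collection was introduced, and reaching Week 12 after it, would have a void-only baseline and possibly a 24-hour Week 12 value. What is at stake is mainly the response rate reported for each arm, because an unmatched subject faces a different effective threshold from a matched one.

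**Working it through.** **Inputs from the documents.** The SD of change in log UPCR is 0.70, with 10 subjects per arm (Protocol 9.4, SAP 2.2.4). Intervals are 90% (SAP 3.1.5). The response threshold is a Week 12/baseline ratio of 0.7.

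**Assumed, not in the documents.** *r*, the ratio of 24-hour to morning-void UPCR in the same subject, is taken as 0.8 to 1.25, the same for all subjects. At *r* = 1 nothing shifts. The SD is varied from 0.60 to 0.80 and is kept the same for mixed pairs.

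**1. The plan's own figure.** Half-width = t(0.95, 18 df) × 0.70 × √(2/10) = 0.543. For a ratio of 0.5 the interval is 0.5 × exp(±0.543) = 0.29 to 0.86. Both match the plan, so 0.70 acts as the SD of an individual subject's change, which is how it is used below.

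**2. Effective cut-off.** Let *t* be the true Week 12/baseline ratio.
- Void baseline, 24-hour Week 12: the recorded ratio is *rt*, so response requires a true fall of at least 1 − 0.7/*r*. At *r* = 0.8 this is 1 − 0.875 = 12.5%; at *r* = 1.25 it is 1 − 0.56 = 44%.
- 24-hour baseline, void Week 12: the requirement is 1 − 0.7*r*, so the two values swap to 44% and 12.5%.

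**3. Probability of response, void baseline with 24-hour Week 12.** P = Φ((ln 0.7 − ln *t* − ln *r*)/SD), with SD 0.70:

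| True ratio *t* | *r* = 0.8 | matched (or *r* = 1) | *r* = 1.25 |
|---|---|---|---|
| 1 (no change) | 42.44% | 30.52% | 20.37% |
| 0.5 | 78.80% | 68.46% | 56.43% |
| Difference, points | 36.36 | 37.94 | 36.06 |

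The last row is the treatment contrast if every subject in both arms were unmatched in this direction. A specimen ratio common to all arms largely cancels against placebo.

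**4. Effect on an arm and on a contrast.** With no true change, each unmatched subject of this type moves the expected rate in an arm of 10 by (42.44 − 30.52)/10 = +1.2 points, or (20.37 − 30.52)/10 = −1.0 point. If one arm has three more such subjects than the other, the difference moves by three times as much: +3.6 or −3.0 points. With SD 0.60 the figures are +4.1 and −3.3; with SD 0.80, +3.2 and −2.8.

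**5. Scale.** For 3 responders of 10, the 90% Clopper-Pearson interval is 8.7% to 60.7%. For 3/10 against 3/10, the 90% Wilson limits are 0.1269 and 0.5583. The unstratified Newcombe half-width is √((0.3 − 0.1269)² + (0.5583 − 0.3)²) = 0.311, or about ±31 points.

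**The case against.** The strongest reply is that the paragraph has a natural paired reading: 24-hour urine is used for the change from baseline to Week 12 when the change can be computed from it. That reading is possible, but it is not stated, and sensitivity analysis 2 shows the same SAP choosing the specimen separately at each end.

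A second reply is that matched versions are already planned. Sensitivity analysis 1 repeats the UPCR analyses on a morning-void baseline with voids preferred afterwards, and could be taken to include the responder table. This is arguable, since the responder paragraph comes later and carries its own specimen rule. The 24-hour-only repeat is attached to the UPCR change summaries. The 24-hour paragraph at the end of SAP 3.4.2 covers analyses derived from spot urine, so its reach over a table that already prefers 24-hour urine is unclear. None of these clearly governs the responder table.

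Other parts of the reply stand. Preferring 24-hour urine here is a legitimate choice; differing from the primary analysis's priority is not a fault. No document shows that any unmatched subject exists: subjects lacking both collections would simply be void/void. Introduction of the collection is not arm-specific under concurrent 1:1:1:1 randomisation, so a 3-of-10 imbalance would be chance. The calculation also ignores subject-to-subject scatter in *r*.

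Three stronger readings are not supported:
- A reader might infer that mixed ratios have occurred or have biased the results. The documents show only that the wording permits them.
- A reader might infer that the primary analysis is free of mixing, or that this point undermines it. Neither follows. The responder wording does not alter the primary analysis, but that analysis's own fallback also substitutes a 24-hour value at either end without a pairing rule. This should be rarer, because it needs a missing void.
- A reader might infer that sensitivity analysis 2 is faulty because it blends specimens. It says that 24-hour results were incomplete and states which specimen is used at each end, so its mixed nature is disclosed.

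**Conclusion.** The gap is real and minor. The responder paragraph lacks a same-specimen condition, and its literal reading allows a mixed ratio. For affected subjects the threshold could move materially, to a true fall of 12.5% or 44% in place of 30%, if the specimens differ by the assumed factor of 0.8 or 1.25. The consequence falls mainly on the response rates within arms. Between arms it is about 3 to 4 points under a 3-of-10 imbalance, well inside an interval of about ±31 points.

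These sizes rest on the assumed *r*, the assumed imbalance and the design SD. The number of unmatched subjects is unknown, and if it is zero or *r* is 1 there is no effect.

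**What to change.** Before database lock, add to the Responder Analyses paragraph of SAP 3.4.1: the 30% reduction is computed from 24-hour values when both Day 1 and Week 12 have one, and otherwise from morning voids at both visits. An unmatched pair is kept, and flagged, only if neither matched pair exists. Report the number of subjects by pair type and arm.

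The cost is one sentence, a change to the derivation code and a small table. A matched pair should nearly always be available: the Time and Events Table schedules a morning void at every visit, and Protocol 7.1 and 7.6 have subjects bring both specimens to Day 1 and Week 12.

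The downside is some lost precision where a lone 24-hour value gives way to a void. The SAP introduces sensitivity analysis 1 with "Given the high variability in morning void spot urine UPCR values", and the protocol's amendment rationale regards the 24-hour measurement as the more accurate. No new model is needed, and the primary analysis and sensitivity analysis 2 can stay as specified.

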6.8. Concomitant Medications and Restrictions

Medications taken prior to enrollment will be recorded:

- **rituximab or other B-cell depleting monoclonal antibodies for 1 year prior to screening;**
Subjects who have taken rituximab or other B-cell depleting monoclonal antibodies but stopped more than 20 weeks before screening will be allowed to participate if the recovery of the B cell population to within normal range is confirmed at the time of screening.
- **all FSGS medications (specifically glucocorticoids, immunosuppressives) for 6 months prior to screening;**

- **all other medications, including plasma therapy regimens, for 12 weeks prior to screening.**

In order not to disrupt subject care, the protocol will allow continuation of treatment (background medications) with glucocorticoids, immunosuppressants, calcineurin inhibitors, or renin-angiotensin-aldosterone system (RAAS) blockers. The doses for these background medications must remain stable for a minimum of 4 weeks prior to screening and through the treatment period (24 weeks) following randomization, with the following exceptions. Adjustment of RAAS blockers is permitted for management of hypertension. During the open label period (after Week 12), glucocorticoids, immunosuppressants, and calcineurin inhibitor will be allowed only if essential for patient safety.

Experimental drugs, rituximab, and plasmapheresis are not allowed at any point during the course of the study. If the Investigator deems that any of these treatments are necessary for the best interest of a subject, this subject would discontinue study drug, but remain in the study to monitor outcomes.

CCX140-B is primarily cleared through CYP3A4 metabolism. Subjects taking strong CYP3A4 inducers (e.g., phenytoin, rifampicin, carbamazepine, St. John's Wort) or strong CYP3A4 inhibitors (e.g., boceprevir, clarithromycin, conivaptan, grapefruit juice, indinavir, itraconazole, ketoconazole, lopinavir/ritonavir, mibefradil, nefazodone, nelfinavir, posaconazole, ritonavir, saquinavir, telaprevir, telithromycin, and voriconazole) will be excluded from this clinical trial since these drugs may substantially increase the CCX140-B plasma levels.

Subjects taking lithium, **pamidronate**, interferon, **or chronic NSAIDS** are also excluded. Note that subjects taking intermittent NSAIDS for pain or fever are discouraged from study participation, but **are** not excluded.

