## 2.2 Study Design

### 2.2.1 Overview

This study will evaluate the efficacy, safety, tolerability, and pharmacokinetics of up to 12 weeks of treatment with each of three dose regimens of CCX140-B or placebo, when used in combination with stable standard of care therapy in subjects with FSGS with significant proteinuria, assessed as UPCR > 1g/g at Screening.

The target is to enroll 40 adult male or female subjects in this randomized, double-blind, placebo-controlled, Phase 2 study. Subjects will be randomized 1:1:1:1 to one of four treatment groups:

- Group A: Placebo (N=10)
- Group B: CCX140-B 5 mg once daily (N=10)
- Group C: CCX140-B 10 mg twice daily (N=10)
- Group D: CCX140-B 15 mg twice daily (N=10)

[figure not shown]
Subjects will be screened within a period not to exceed 28 days prior to Study Day 1 (the first day of dosing). All subjects will take blinded study medication in the morning and evening, with or without food, for 84 consecutive days. Following the 84-day blinded dosing period, all subjects will take open label CCX140-B for an additional 84 days at the highest dose under evaluation, currently planned to be 15 mg twice daily.

During the treatment period, eligible subjects will visit the study center on Study Days 1, 8, 15, 29 (Week 4), and Weeks 8, 12 (primary endpoint), 13, 16, 20, and 24 for study procedures including interval history, physical examination and vital signs, ECG, study questionnaires, and collection of blood and urine. Subjects will discontinue study drug as of Study Day 169 (Week 24) and will return for a follow up visit on Week 28. When feasible, upon discontinuation of treatment for any reason a sample of whole blood should be collected for assessment of elimination 2, 7 and 14 days after the final dose of CCX140-B (or placebo).

A study schema is depicted in Figure 1. All study procedures are presented in Table 1.

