### *3.2.3 Per-Protocol (PP) Population*

The PP Population is defined as all subjects in the ITT Population who have  $\geq 80\%$  compliance with the study drug administration and do not have protocol deviations that could significantly affect the interpretation of the results for the primary endpoints. The PP Population will be a secondary population for analysis of the primary efficacy endpoint.

The following aspects will be considered for subjects to be excluded from the PP analysis:

- Subjects with significant protocol deviations regarding inclusion and exclusion criteria that may impact evaluation of the primary endpoints.
- Subjects with significant lack of compliance of study medication administration (CCX140-B /placebo) defined as: All subjects who were  $<80\%$  compliant with taking CCX140-B /placebo based on study medication accountability records.
- Subjects administered non-protocol allowed medications such as, calcineurin inhibitors, ACE-inhibitors or ARBs, spironolactone, eplerenone, antihypertensive, diuretics, immunosuppressants or calcineurin inhibitors or subjects with dose increases of such drugs during the course of the study.

Subjects to be excluded from the PP population will be identified and documented prior to the database lock and unblinding for analysis. A subject's data could be partially excluded from analysis depending on when the deviation occurred. For example, if a deviation occurred during the open-label extension (OLE) that did not impact the data from the double-blind period, only the data during the OLE will be excluded.

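### The non-responder rule for the Week 12 responder analysis has no time limit, so a non-allowed therapy first given after Week 12 can turn a Week 12 responder into a non-responder

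*SAP*

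**What the plan says.** The responder analysis in SAP section 3.4.1 is tied to one time point: the rate of subjects with a 30% UPCR reduction "from baseline at Week 12 will be calculated". The paragraph on non-allowed medications then covers "All subjects who started new therapy or increased the doses of an existing therapy that is clinically significant and was not allowed per protocol"; these subjects "will be imputed as non-responders for the responder analysis". It names no visit, study day or period. The one further step is that new use or clinically significant increases of RAAS blockers, and new use of glucocorticoids, calcineurin inhibitors or other "immunomodulatory or immunosuppressive therapy will be reviewed before database lock".

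Two other medication rules in the SAP do refer to time:

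- Sensitivity analysis 3 (section 3.4.1): "all data after the initiation of the non-allowed medication will be imputed using the last observation prior to the initiation" of that medication. Values before the start are left alone.
- Per-protocol population (section 3.2.3): a subject's data may be excluded in part. The example given is an open-label deviation that left the double-blind data unaffected, where "only the data during the OLE will be excluded".

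The study continues well beyond Week 12. SAP section 2.2.1 says that "all subjects will take open label CCX140-B for an additional 84 days". Protocol section 6.8 says that background doses "must remain stable for a minimum of 4 weeks prior to screening and through the treatment period (24 weeks"), with stated exceptions, and bars experimental drugs, rituximab and plasmapheresis for the whole study.

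**The concern.** A Week 12 response is a randomised, blinded outcome. A therapy first given after the Week 12 urine was collected cannot have produced it, so there is no reason to treat that response as contaminated. A rule without a time limit nevertheless lets an open-label or follow-up event overwrite it.

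By then the continuing subjects are planned to be on a common open-label dose, and the placebo and lower-dose subjects have changed treatment. Whether a subject later starts another therapy then depends on events outside the blinded comparison. With 10 subjects per arm, one reclassification is enough to move an interval across zero. Two programmers working from this paragraph could also report different response rates.

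**Working it through.** **Step 1. Can the situation arise?** Four conditions are needed, and the documents supply each.

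1. Some therapies are still non-allowed after Week 12. Protocol 6.8 bars rituximab, experimental drugs and plasmapheresis throughout. In the open-label period it allows glucocorticoids, immunosuppressants and calcineurin inhibitors only when essential for patient safety.
2. The subject's data remain in the study. Under Protocol 6.8, a subject who needs a barred treatment stops study drug but stays in for outcomes.
3. The later medication is recorded. The Time and Events Table and Protocol 7.12 collect concomitant medications up to the follow-up visit (Week 28, or Week 16 for subjects who do not continue).
4. The later medication is in the database when the rule is applied. SAP 5.1 plans no interim analysis, and SAP 5.2 describes one final analysis on the finished database. Protocol section 9 mentions an analysis after Day 85 as well, but the SAP supersedes it.

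**Step 2. One subject under the three rules.** Suppose a subject meets the 30% criterion at Day 85 with no medication change and first receives rituximab on Day 130.

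| Rule | Effect on the Week 12 value |
|---|---|
| Sensitivity analysis 3 | Kept; only values after Day 130 are replaced |
| Per-protocol population | Can be kept; the text allows exclusion of open-label data alone |
| Non-responder rule, as written | Overridden; counted as a Week 12 non-responder |

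**Step 3. Size.** The SAP states no figure for the responder analysis. Its sample-size figure confirms the setting of 10 per arm and two-sided 90% intervals: t(0.95, 18 df) × SD × √(2/10) = 1.734 × 0.70 × 0.4472 = 0.543, as stated in SAP 2.2.4. For a ratio of 0.5 this gives 0.5 × exp(±0.543) = 0.29 to 0.86, also as stated.

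Each recoded subject moves an arm's rate by 1/10 = 10 percentage points. The documents give neither response rates nor a rate of late non-allowed use, so the counts below are assumptions. The interval is the unstratified Newcombe hybrid-score interval. Here l and u are the Wilson 90% limits for each arm (z = 1.645), p1 and p2 are the active and placebo rates, and d = p1 − p2:

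- lower = d − √[(p1 − l1)² + (u2 − p2)²]
- upper = d + √[(u1 − p1)² + (p2 − l2)²]

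Wilson limits for n = 10 are: 6/10, 0.3516 to 0.8058; 5/10, 0.2693 to 0.7307; 2/10, 0.0686 to 0.4592; 1/10, 0.0226 to 0.3477.

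For 6/10 versus 2/10, lower = 0.40 − √(0.2484² + 0.2592²) = 0.041 and upper = 0.40 + √(0.2058² + 0.1314²) = 0.644. The other rows follow in the same way.

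| Case | Active vs placebo | Difference | 90% CI |
|---|---|---|---|
| Rule limited to before the Week 12 collection | 6/10 vs 2/10 | 0.40 | 0.041 to 0.644 |
| One active responder recoded for a later start | 5/10 vs 2/10 | 0.30 | -0.047 to 0.566 |
| One placebo responder recoded for a later start | 6/10 vs 1/10 | 0.50 | 0.149 to 0.720 |

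One recoded subject shifts the difference by 0.10 either way. In the second row the interval comes to include zero.

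**The case against.** The strongest reply is that the paragraph sits under an analysis whose only time point is Week 12 and that a pre-lock review is built in, so a sensible team would apply the rule to the blinded period alone. That may happen. But the review has no stated window, and neither time-aware rule is written to govern this one. The contrast with sensitivity analysis 3 is firm. The per-protocol contrast is weaker, because that text is permissive and offered as an example. The contrasts suggest an omission without proving what the authors intended.

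A second reply is that few subjects will be affected, and this stands. The therapy must be both clinically significant and non-allowed. A reader might infer that any new calcineurin inhibitor, glucocorticoid or immunosuppressant in the open-label period triggers the rule. The documents do not support that: Protocol 6.8 allows these when essential for patient safety, so they count only where that exception is not met. RAAS adjustment for hypertension is also permitted, and Protocol 5.4 requires that extension entrants have no anticipated need for new immunosuppression over the next 12 weeks.

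A reader might also infer that the rule systematically shrinks the difference from placebo. That would follow if late starts were equally frequent in both arms and independent of response, but the documents give no such rates and independence is doubtful. Subjects whose proteinuria has fallen may need added therapy less often.

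**Conclusion.** The concern holds as a defect in the written rule. Applied literally, it gives a wrong Week 12 classification for any responder whose first non-allowed therapy comes after the Week 12 urine collection. Each such subject moves an arm's rate by 10 percentage points, on the planned 10 per arm. The direction of the bias is unknown, and the number of such subjects may be small or zero. The intervals shown rest on assumed counts and omit the planned stratification.

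The reach is limited. SAP section 6 lists the responder analysis as an addition to the protocol's analyses, and SAP 3.1.5 calls the study exploratory. It would be wrong to infer that the primary result is compromised, because the primary MMRM does not use this rule. Nor does SAP 3.4.2 expressly extend the rule to the remission endpoints. The change should be made because it is nearly free and removes an avoidable ambiguity before unblinding.

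**What to change.** Add a time limit to the non-responder paragraph in SAP 3.4.1. For the Week 12 response, only non-allowed starts or dose increases that occurred after the first dose of study drug and before completion of the urine collection used for the Week 12 UPCR lead to non-responder status. If the rule is also meant for Week 24 responses, say so and use the Week 24 collection there.

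The cut-off should be the collection and not the visit date. The responder analysis prefers 24-hour urine, and under Protocol 7.6 that collection ends with the first morning void on the day of the Week 12 visit. A cut-off of on or before the visit date would still recode a therapy started at the visit, after the urine was complete. The SAP should also state how a same-day start is handled when only a calendar date is known.

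The cost is one clause in the SAP and one date comparison in the program. Sensitivity analysis 3 already needs the initiation date of each non-allowed medication, so the change adds little or no data requirement.
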